Official title: Impact of carbon fiber AFOs on gait and resulting changes in quality of life across time in persons with PD

NCT number: NCT03192046

IRB Approved date: February 15, 2017

**The University of Texas Southwestern Medical Center at Dallas
Institutional Review Board**

Protocol

Title: Impact of carbon fiber AFOs on gait and resulting changes in quality of life across time in persons with PD

1. Introduction and Purpose:

Parkinson disease (PD) is a progressive neurological disease that results in characteristic gait dysfunction. Gait problems include decreased velocity, decreased stride length, difficulty with initiation of gait, postural stability problems and alteration in joint kinematics.¹ In this typically older patient population, these gait deviations affect their participation in household and community activities. The standard of care is currently focused on therapeutic exercise and cueing of various types (visual, auditory, verbal). Current interventions have not been demonstrated to markedly improve gait kinematics, so there is a need to identify interventions that could improve gait performance in this population. Lower extremity bracing is a common and well-established intervention for gait dysfunction with other populations, including stroke and brain injury. The braces allow for improved stability, sensory feedback, and consistent tactile cues to allow patients to have the best gait mechanics with each step. It is reasonable to hypothesize that appropriate bracing may have the potential to improve gait function and kinematics in PD since these patient often have gastroc-soleus weakness. Data from our early pilot studies indicates that bracing individuals with PD can positively impact their mobility. This includes improvements in velocity, step length, and dynamic balance. Additional data supported an upward trend in quality of life.

The purpose of this study is to investigate the impact of a specifically designed ankle foot orthosis (a custom fabricated carbon fiber brace) on the spatial and temporal gait parameters, kinematics, and walking endurance in individuals with Parkinson's disease. The brace utilized will be chosen according to patient need and presentation. The carbon fiber orthosis is fabricated to allow ankle range of motion while providing external stability and energy storing qualities.

This study has three hypotheses. 1) subjects who are fit with carbon fiber orthoses will demonstrate better spatial and temporal gait parameters compared to controls; 2) subjects who are fit with carbon fiber orthoses will demonstrate improvements in gait kinematics during gait as compared to controls, and 3) as a result of the improvements in their mobility, subjects fit with carbon fiber orthoses will have an overall improvement in their quality of life compared to controls.

2. Background:

Parkinson's disease results in a variety of functional impairments including weakness, gait dysfunction and postural changes. Exercise has been a key tool in the treatment of such limitations, although there is not robust evidence supporting any specific type of intervention in the management of PD.² There is some evidence that exercise in general can be beneficial regarding quality of life, strengthening, balance and gait speed but optimum dosing and exact content of the ideal intervention has not been identified.³ Gait dysfunction is one of the most disabling effects of PD yet clear direction on how to treat this problem is lacking. While there is evidence of brain disturbances leading to gait problems⁴ it is also acknowledged that weakness and sensory loss are significant contributors to gait dysfunction in PD.¹

Orthotic management of gait disturbance in diagnoses such as stroke and brain injury is common as such devices have the potential to address weakness as well as sensory impairment. However, the potential role of bracing in PD has not been explored in the literature. This study is designed to

evaluate the effectiveness of bracing on some of the common manifestations of gait dysfunction in PD.

3. Concise Summary of Project:

This is a randomized, repeated measures, matched group study. There will be two groups of participants, 8 participants per group, 35 participants total from time of initial enrollment in this study. Group one (G1) will receive bilateral custom braces and a standardized home walking/exercise program. Group two will receive the standardized walking/exercise program without any brace or AFO. Subjects will be randomized upon enrollment in the study. At the time of consent, random drawing from concealed envelopes with red, blue or green chips will be done to determine group assignment. Subjects will be recruited through the Clinical Center for Movement Disorders at UT Southwestern Medical Center where patients with PD receive routine evaluation and follow-up. Subjects will be followed for 6 months during this study and outcome measures will be collected 3 times over the course of the study. Subjects will be seen every 3 months for the duration of the study for testing as well as for other visits as noted in the table below. Participants will not need to have insurance benefits for initial physical therapy evaluation and for ankle braces. All subsequent visits to the Crowley gait lab for assessments and brace adjustment will be provided at no cost to the participants.

Outcome measures

Testing Procedures:

6-Minute Walk Test: Each subject will be asked to walk at a self-selected velocity on level surfaces for 6 minutes. They will be allowed to use assistive devices if necessary.

Computerized Gait Analysis: Each subject will be asked to walk on a 12-16 foot long vinyl pad placed on the floor. The mat will record and analyze temporal and spatial gait parameters.

Observational Gait analysis: Gait will be evaluated using the Observational Gait Analysis system during over ground walking. A sample of the gait will be videotaped for detailed analysis.

Three-Dimensional gait analysis: Prior to testing, subjects will be outfitted with small retro-reflective markers secured to anatomical locations with easily removable tape. Once markers have been positioned properly, the subject will then be asked to walk up and down a level 15-foot walkway. Four walking trials will be recorded for averaging purposes.

Four Square Step Test: Balance while stepping in different directions will be assessed using this test. Skills such as stepping over an obstacle and stepping backwards are included in the test.

Falls data: Patients will be asked to fill out a fall log at home.

Short Orientation-Memory-Concentration Test of Cognitive Impairment: Gross cognitive function will be tested using this brief questionnaire.

Daily Activity: Steps per day recorded from a pedometer the patients will wear for the week prior to each testing visit. Daily walking (steps/day) will be recorded throughout the study.

PDQ-39: The PDQ-39 is the most widely used Parkinson's Disease specific measure of health status. It contains thirty nine questions, covering eight aspects of quality of life. The instrument was developed on the basis of interviews with people diagnosed with the disease. It has been widely validated, and translated into over fifty languages.

4. Study Procedures: -

Screening, consent and randomization	Confirm medical diagnosis and medical history, assess sensation and range of motion. Consent process. Appointment made for casting.	60 minutes
Baseline Testing (T1)	Initial outcome measures completed with no	120 minutes

	orthoses and first set of orthoses.	
Visit 1 - 4 Month 1	Gait training session. Instruct in home walking program.	45 minutes
Visit 5 – Month 2		
Testing 2 (T2) – Month 3	All outcome measures completed.	120 minutes
Visit 6 and 7- Month 4 & 5	Gait training session.	45 minutes
Testing 3 (T3) – Month 6	All outcome measure completed	120 minutes

The gait training home program is outlined as follows:

- One to two bouts of focused walking per day. Regardless of the number of walking bouts, the goal is 30 minutes total per day.
- Increase the bouts by 2-5 minutes as tolerated working up to 30 minutes total
- Each subject will receive individualized tape walking protocol based on GAITRite data
- Each subject will receive standard instructions for a home exercise program and will receive handouts

5. Sub-Study Procedures:

There are no sub-studies.

6. Criteria for Inclusion of Subjects:

1. Confirmed diagnosis of Parkinson's Disease according to the UK brain bank criteria.⁵
2. Age between 30 and 85.
3. Measurable decrement in gait velocity (between 35 and 15 percent below age-predicted norms for self-selected walking velocity) as measured by the 6 MWT
4. Hoehn and Yahr stage 2-3.
5. Less than 10 full heel raises in single limb stance bilaterally.

7. Criteria for Exclusion of Subjects:

1. Body mass index greater than 40.
2. Passive dorsiflexion range of motion less than approximately neutral (90 degrees)
3. Any other uncontrolled health condition for which gait training is contraindicated
4. Self-report of > 1 fall/month
5. A score of 11 or less on the Short Orientation-Memory-Concentration Test of Cognitive Impairment

8. Sources of Research Material:

Some data will be extracted from the medical record to provide needed information prior to treatment. This includes: prior medical history, confirmation of Parkinson's diagnosis, medication history and use. The dependent assessments include: The outcome measure for the study include: 1. GAITRite System for temporal and spatial parameters, 2. Kinematics, 3. 6-Minute Walk Test (gait endurance), 4. Four Square Step Test, 5. Video tape of over ground gait analysis, 6. PDQ-39 (Parkinson's Disease Questionnaire 8), 7. Falls data; 8. Daily activity (pedometer).

9. Recruitment Methods and Consenting Process:

Subjects will be recruited through the Clinical Center for Movement Disorders at UT Southwestern Medical Center where patients with PD receive routine evaluation and follow-up. Each participant will be scheduled to attend an initial meeting at the School of Health Professions Gait Disorders Clinic. The research project will be explained by [name] using the Subject Consent Form as a guide and participants will be randomized to the groups following consent. If they are candidates. This meeting will take approximately 90 minutes. A second visit will be scheduled for the initial assessments and this will take approximately 120 minutes. The original consent and HIPAA Authorization will be maintained in the research file, and the participant will receive a copy of each.

10. Potential Risks:

There is minimal risk involved in participating in this study. There may be minor skin irritation as the result of the new brace(s) as well as minor skin irritation from the surface electrodes used in the EMG testing. There may be minimal fatigue associated with the walking and testing sessions.

11. Subject Safety and Data Monitoring:

The participant's identity will be kept in a separate locked file cabinet in the David M. Crowley Research and Rehabilitation Lab. The subjects will be closely monitored during treatment and testing.

12. Procedures to Maintain Confidentiality:

Each participant will be assigned a unique identification number once it has been determined that the person meets the inclusion criteria and has signed the consent form and HIPPA authorization form. The unique number will be used to identify all data sets for the individual participant. De-identified information obtained during this study will be released to requesting agencies only with a written release of information from the participant. The results of this research may appear in scientific publications but the participants' names will not be used. All data will be maintained in a research folder in a locked cabinet in the David M. Crowley Research and Rehabilitation Laboratory. The UT Southwestern Institutional Review Board is responsible for assuring that participants' rights are respected. Members of the staff may review records for audit purposes. That review will take place at The Department of Physical Therapy.

13. Potential Benefits:

It is anticipated that the application of this orthosis will result in an immediate improvement in gait parameters (temporal and spatial) as well as long term improvements in activity and gait tolerance as well as balance and strength.

14. Biostatistics:

The proposed design thus consists of two treatment groups ("between" effect) with 8 patients (subjects)/group studied over 3 test sessions ("within" effect). At each data point, nine classes of measures are to be obtained, e.g., the 6-minute walk test, computerized gait analysis, etc. Some of these classes may yield more than one measure. We propose four groups of analyses.

Intent to treat analysis.

Not all patients who initially consent and are randomized may complete the study. We plan to compare (a) those that finish with those who do not finish to see if they differ with respect to any of the dependent variables and (b) the proportions of those who do not finish to see if they are equally divided among the groups. The former will be compared by means of *t*-tests or its nonparametric

counterpart, the Mann-Whitney U, depending upon how well normality assumptions are met. The latter will be compared by means of chi-square or Fisher exact test depending upon sample size. Preliminary psychometric analyses.

We feel it important to evaluate the relations among the various classes of dependent variables by intercorrelating them to infer their structure, e.g., how many dimensions do they span and are any sufficiently redundant so they can be combined. This involves standard item analysis and exploratory factor analysis. Similar analyses will be performed on the scores obtained from the inclusion measures and other demographics, e.g., can the Hoehn and Yahr scores be combined with other measures to obtain a composite impairment measures that can serve as a better covariate.

Analysis of observed measures

If all patients who complete the study do so without missing any of the test sessions, ordinary repeated measures analysis of variance (ANOVA) will be used to evaluate the main effect of groups, the main effect of testing sessions, and their interaction. Planned comparisons will be employed comparing (a) groups G1 and G2 with each other. This involves comparing what in effect are two control conditions with each other and their average against the active treatment condition. This will be done as a series of univariate tests.

Next, we will examine the effects of covariates such as age of onset and impairment as inferred through the Hoehn and Yahr scale and other measures, again in a univariate manner.

We will then perform a multivariate analysis of variance (MANOVA) to test the null hypotheses that differences on the three effects of interest (groups, testing session, and their interaction) are all nonsignificant across the set of dependent variables.

It is quite likely that there will be missing data from patients who fail to attend one or more testing sessions. We will deal with this problem in two ways. One is to attempt to impute the missing data (see next subsection). The other is to use a mixed model (random regression) which does not require all data to be present, e.g. can analyze the testing effect using whatever data are present. This allows for the same univariate tests to be conducted, but makes multivariate testing extremely difficult to impossible with the data as obtained.

Analysis of imputed measures

Assuming there will be missing data, we will attempt to impute the missing data and perform the analyses as listed in the previous section, including the MANOVA, on these imputed data.

References

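### Chip draw at the consent meeting leaves the allocation order unprotected and unauditable; a pre-generated list in numbered, sealed, logged envelopes is a cheap improvement

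*Combined protocol and SAP*

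**What the plan says.** Section 3 (Concise Summary of Project) says "Subjects will be randomized upon enrollment in the study" and that, when consent is given, "random drawing from concealed envelopes with red, blue or green chips will be done to determine group assignment". Section 9 (Recruitment Methods and Consenting Process) agrees: at the initial meeting "participants will be randomized to the groups following consent", and "A second visit will be scheduled for the initial assessments".

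The counts are in two places. Section 3: "There will be two groups of participants, 8 participants per group, 35 participants total from time of initial enrollment in this study". Section 14 (Biostatistics) describes two treatment groups "with 8 patients (subjects)/group studied over 3 test sessions", and adds that some randomised patients may not complete.

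One arm receives bilateral custom braces with the home programme, the other the home programme alone. The documents do not mention blinding.

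They do not say how many envelopes there are, whether drawn ones go back, who prepares and holds them, whether they are numbered or logged, or which colours stand for which group. Section 3 calls the design matched but gives no matching or blocking rule.

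**The concern.** Concealment has two parts: the next assignment must be hidden, and it must not be possible to infer or change it. The text covers only the first. In a pool of unnumbered envelopes there is no fixed order to check against, and the plan describes no record that would show a repeated draw.

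Earlier assignments are knowable because a brace cannot be hidden from staff. If the pool is not refilled, those assignments carry information about the next one. The eligibility bands leave some room to act on a guess: walking velocity 15 to 35 percent below the age norm, and Hoehn and Yahr stage 2 to 3 (section 6).

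The order of steps adds to this. Section 6 defines the velocity criterion by the 6-minute walk test, but the combined screening, consent and randomisation row in section 4 lists only diagnosis, history, sensation and range of motion. Section 9 puts the initial assessments at a second visit. As written, an eligibility measurement may therefore follow the draw, so that the decision to keep a borderline patient is made with the arm known.

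At stake is whether the two groups are comparable at entry. With about 8 per group, a baseline comparison has little chance of revealing a modest selection effect.

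**Working it through.** The plan contains no calculation on this point, so there is no figure of its own to reproduce beyond the counts: 2 × 8 = 16, which is not 35. Nor is 3 × 8 = 24, if the three colours reflect three arms.

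**Inputs.** From the documents: two groups, 8 per group, 35 in total. Assumed, because not stated: 1:1 allocation, and the envelope pools below.

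**A. Drawn envelopes are set aside.** The observer knows the pool and past draws and always guesses the arm with more envelopes left.

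- 8+8 pool, expected correct guesses: n + (4^n / C(2n,n) − 1)/2 with n = 8. This is 8 + (65,536/12,870 − 1)/2 = 8 + 4.092/2 = 10.05 of 16, or 63%, against 50% by chance.
- Draws that are certain at the end, for a pool of a+b: a/(b+1) + b/(a+1). For 8+8: 8/9 + 8/9 = 1.78. The last draw is always certain; the last two are in 47% of trials and the last three in 20%.
- 17+18 pool: 20.8 of 35 correct by simulation (59%). Certain draws: 17/19 + 18/18 = 1.89.

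**B. Envelopes are returned (independent fair draws).**

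- Exactly 16 randomised: P(8/8) = C(16,8)/2^16 = 12,870/65,536 = 19.6%. P(11/5 or worse) = 21.0%.
- Relative efficiency of a split a/b against 8/8 is 4ab/16². For 9/7: 252/256 = 98%. For 10/6: 240/256 = 94%. For 11/5: 220/256 = 86%.
- All 35 randomised: both arms receive at least 8 with probability 99.95%. The probability that both keep at least 8 completers depends on retention, which the documents do not give:

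| Retention (assumed) | Both arms keep at least 8 |
|---|---|
| 80% | 98.0% |
| 70% | 91.6% |
| 60% | 73.9% |
| 50% | 42.0% |

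**C. What a guess could do to the result.** Suppose the recruiter acts on every guess, always in the same direction, by inviting a patient η SD better or worse. For the 8+8 pool there are 10.05 right and 5.95 wrong guesses, so the expected null difference is 2η × (10.05 − 5.95)/16 = 0.51η. That is 0.13 SD at η = 0.25 and 0.26 SD at η = 0.5. For 17+18, simulation gives 0.09 and 0.18 SD. A two-sample t-test at two-sided 5% then rejects a true null in about 5.5% of trials at η = 0.25 and about 7% at η = 0.5, for either pool. The values of η are assumptions, and this test is not the planned analysis.

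**D. Would small blocks do better?** Over 16 assignments, always guessing the arm with fewer patients so far is right 71% of the time with known blocks of 4, and 69% with random blocks of 2, 4 and 6. Small blocks alone are more guessable than the 8+8 pool. What matters more is keeping the sequence away from those who screen and consent.

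**The case against.** The strongest objection is to a reading that a reader might infer: that the procedure must fail either way, because staff can predict the next arm or else 8 per group is usually not delivered. The documents do not support it. It needs exactly 16 randomised, while section 3 also gives 35 in total and section 14 expects losses after randomisation. If 8 means completers, independent draws usually suffice at retention of 70% or more. Even with 16 randomised, missing 8/8 by one or two patients costs 2% to 6% of efficiency. This part of the objection stands.

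Prediction is also limited. Only the last one or two draws are certain on average. Before that it is a better-than-chance guess, and it requires knowing the pool. The documents do not say that recruiters see the draws, or that the same people recruit, train and test. This stands too.

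On bias, section 14 plans repeated-measures ANOVA over three sessions including baseline, with covariates. A stable shift in patient type cancels from the group-by-session interaction, though it would still affect the group main effect. So the figures under C are illustrations, and a claim that a group difference would simply be taken for a brace effect goes too far.

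On the order of steps, section 9 conditions randomisation on being a candidate, and section 12 assigns the study number once inclusion criteria are met and consent is signed. Both suggest that eligibility is settled early. Neither says when the 6-minute walk for eligibility is done, so the point remains as a possibility.

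None of this supplies a fixed order, a custodian or a record.

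**Conclusion.** The concern holds as a case for a cheap and better method. The stated draw hides the chip but leaves the order neither protected nor auditable, in a trial where the assigned arm is plain to see. That the trial is unblinded is inferred from brace versus no brace, but no other reading is practical.

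If envelopes are set aside, about 63% (8+8) or 59% (17+18) of assignments could be guessed against 50% by chance, assuming 1:1 allocation and an observer who knows the pool and past draws. If they are returned, guessing is no better than chance, and the 20% chance of 8/8 applies only when exactly 16 are randomised. Any bias rests on an assumed selection strength and is probably modest. Predictability and the missing audit trail weigh more than imbalance.

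Neither balance nor concealment can be fully judged until 8 per group is reconciled with 35 in total and the three colours with two groups.

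**What to change.** Replace the chip-draw sentence in section 3 with the following procedure, and align sections 4 and 9.

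- Generate one two-arm list by computer before enrolment starts.
- Place the assignments in sealed, opaque, sequentially numbered envelopes, prepared and held by an existing department member who does not recruit, consent or test.
- Open the next envelope only after consent and all eligibility results, including the 6-minute-walk velocity, are recorded, with the patient's ID written on the envelope. List that measurement in the screening row of section 4.
- Keep a log of envelope number, date and ID.
- Leave the choice of any balancing rule to the statistician, and keep its details out of documents that the recruiter sees.
- Remove the three-colour wording.
- State which of 8 per group and 35 in total is the number randomised and which the number expected to complete.

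Cost: a one-paragraph amendment with matching edits, and about an hour to prepare the list and envelopes. No new staff or visits are needed, provided the 6-minute walk for eligibility fits into the screening meeting. The final split may not be exactly equal, which costs little precision.

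### No masking is described for the observer-rated gait analysis, although only one arm wears braces and the planned tape could be scored from coded, shuffled clips

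*Combined protocol and SAP*

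**What the plan says.** Section 3 (Testing Procedures) states that "Gait will be evaluated using the Observational Gait Analysis system during over ground walking" and then that "A sample of the gait will be videotaped for detailed analysis". It does not name the rater, the items or the scale, and it does not say whether the live or the taped rating is the one analysed. Section 8 lists the outcomes and includes "5. Video tape of over ground gait analysis".

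The arms differ visibly: "Group one (G1) will receive bilateral custom braces and a standardized home walking/exercise program", while "Group two will receive the standardized walking/exercise program without any brace or AFO".

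The Section 4 visit table gives an orthosis condition for T1 only. That row starts "Initial outcome measures completed with no" and continues across a table break to cover testing without orthoses and with the first set. For T2 it says only "All outcome measures completed", and T3 is worded in the same way.

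The one concealment step in the document concerns allocation: a "random drawing from concealed envelopes with red, blue or green chips". Nothing is said about masking an assessor, a tape reader or an analyst.

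**The concern.** Among the gait measures, this one rests on a person's judgement; the mat and the marker system record by instrument. Four conditions for detection bias are present together: a judged score, a device worn in one arm only, a protocol that expects benefit (Sections 1 and 13), and no described masking.

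Section 14 does nothing to contain the effect. No primary outcome is named. Each measure is tested for group, session and interaction effects, the set is then tested jointly by MANOVA, and redundant measures may be combined. A rating shifted by expectation can therefore show as a brace effect on its own and can feed into a global or composite result. Timed and instrumented results cannot be re-read by a masked person afterwards, but a tape can.

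**Working it through.** **1. Is it an analysed outcome?** Section 3 and its continuation describe nine measures: 6-minute walk, computerized mat, observational gait, 3D gait, Four Square Step, falls, the cognitive test, daily activity and PDQ-39. Section 14 speaks of nine classes of measures, so the observational rating is among them. Section 8 lists eight outcomes, and the tape is number 5. Both counts include it.

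**2. Where would a rater shift appear?** Let *b* be the amount added to a G1 rating when the rater sees the brace, with no true effect. The expected G1 minus G2 differences at T1, T2 and T3 depend on the orthosis condition, which the plan leaves open at T2 and T3:

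| T1 baseline used | T2 and T3 | Differences | Group effect (mean of three) | Change from T1 |
|---|---|---|---|---|
| no orthosis | brace on | 0, *b*, *b* | (0 + *b* + *b*)/3 = 2*b*/3 | *b* |
| brace on | brace on | *b*, *b*, *b* | *b* | 0 |
| no orthosis | brace off | 0, 0, 0 | 0 | 0 |

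In the first row the bias enters both the group effect and the interaction. In the second it enters the group effect only. In the third there is no shift from seeing the brace, although a rater who knows the arm could still favour it. Whether the bias arises, and in which test, therefore turns on something the plan does not state.

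**3. How large could it be?** The plan gives no figure to reproduce: no alpha, SD, rating scale or rater agreement. The following is illustration only. Inputs: 8 per group (Section 14); assumed two-sided 5% test, no true effect, and a shift *d* in SD units. For a two-sample t-test, df = 8 + 8 − 2 = 14 and the noncentrality is *d* × √(8 × 8/16) = 2*d*.

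| Assumed shift (SD) | Noncentrality | Rejection rate |
|---|---|---|
| 0 | 0 | 0.050 |
| 0.25 | 0.5 | 0.075 |
| 0.5 | 1.0 | 0.154 |
| 1.0 | 2.0 | 0.461 |

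This models one timepoint, whereas the plan uses repeated measures. For change from an unshifted T1 with within-subject correlation *r*, the change has SD √(2(1 − *r*)), so the noncentrality is 2*d*/√(2(1 − *r*)). With *d* = 0.5:

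- *r* = 0.2: noncentrality 0.79, rejection 0.11
- *r* = 0.5: noncentrality 1.00, rejection 0.15
- *r* = 0.8: noncentrality 1.58, rejection 0.31

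With *d* = 0.1 the rate stays at 0.05 to 0.06 over the same correlations. The answer depends almost wholly on *d*, and the documents do not inform *d*.

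**4. What can a tape mask?** Session and visit order can be hidden on any clip by coding and shuffling. Arm can be hidden only where no orthosis is worn, because a brace that a live rater sees is normally visible on tape too.

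**The case against.** The strongest reply is that the plan is silent and does not specify unmasked rating. A reader might infer that follow-up ratings are made with the brace in plain view by someone who knows the session. The documents do not say so: the orthosis condition at T2 and T3 is not given, nor is what the rater knows. T1 already includes a with-orthosis condition, so on one reading a constant shift would cancel from the interaction (second row of the first table). This stands, and the point is limited accordingly to masking not being described.

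A reader might also take the 15% or 46% as this trial's false-positive rate. That is not supported. The shifts are assumed, and the single-timepoint test is not the planned analysis.

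A third tempting inference is that the tape makes full masking available at almost no cost. The documents give no cost, and a tape does not hide a brace. Covering the lower legs would obscure the joints being rated and sits badly with marker-based capture at the same visits. It would change the measure as well as mask it.

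Finally, hypotheses 1 and 2 are served by the mat and the 3D system and hypothesis 3 by the PDQ-39, so no hypothesis rests on this rating alone. This limits the consequence. It does not remove it, because the rating is still tested and still enters the MANOVA.

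**Conclusion.** The concern holds in a limited form. A judged outcome is compared between a braced and an unbraced arm with no masking described, and it enters the group-by-session tests and the MANOVA. Rater expectation could favour the brace on this outcome and on any global test or composite containing it. The direction is inferred from the benefit the protocol anticipates. The size cannot be estimated from the documents; the rates above show only what assumed shifts would do. The instrumented mat and 3D measures are much less exposed. The change is worth making because scoring the planned tape from coded clips avoids part of the bias, but the point does not undermine the trial's main gait measures.

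**What to change.** Settle the following before filming starts, because what was not filmed cannot be recovered later:

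1. Make the tape score, not the live rating, the analysed outcome, and state the items and scale.
2. Film every subject in both arms at T1, T2 and T3 in a stated orthosis condition, with a no-orthosis clip where the visit allows, as T1 testing already does.
3. Label clips with random codes. After the last T3 visit, have existing study staff score all clips in one shuffled batch, preferably someone not involved in that subject's gait training.
4. Withhold identity and session on all clips, and arm on the no-orthosis clips.
5. Report between-group results from clips in which the brace shows as unmasked.

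Withholding session helps even on braced clips. A reader who cannot tell T1 from T3 has no basis for scoring expected improvement over time.

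**Cost.** No extra visits or staff are needed, but there is reading time, and an additional clip has to fit within the 120-minute test session. Scores arrive only at study end. With 8 per group, a reader may recognise subjects. Arm cannot be masked where the brace is visible. A no-orthosis comparison at T2 and T3 describes unbraced gait after a period of brace use, not walking in the brace, so the two kinds of clip should be reported separately.
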